## 10.7 APPENDIX 7: CRS TOXICITY TREATMENT GUIDELINES

Note these as guidelines may require modification based on clinical circumstances of each subject. The investigator should consider both best outcome for the subject and institutional standard of care treatment protocols. As such failure to exactly follow these guidelines is not a protocol deviation or violation as follows:

Cytokine Release Syndrome Grading Assessment (Lee, 2019)	Corticosteroids
Grade 1: Symptoms are not life-threatening and require symptomatic treatment only (fever, nausea, fatigue, headache, myalgias, malaise)	
 
• N/A
 

Grade 2: Symptoms require and respond to moderate intervention: 
 
• Oxygen requirement <40% FiO2 OR
 
• Hypotension responsive to IV fluids or low dose of one vasopressor OR
 
• Grade 2 organ toxicity*
 
	
 
• Vigilant supportive care with careful monitoring of cardiac and other organ function
 

Grade 2: As above but with extensive co-morbidities or older age. OR Grade 3: Symptoms require and respond to aggressive intervention: 
 
• Extensive co-morbidities or older age
 
• Oxygen requirement <math>\geq 40\%</math> FiO2 OR
 
• Hypotension requiring high-dose or multiple vasopressors OR
 
• Grade 3 organ toxicity* or Grade 4 transaminitis
 
	
 
• Administer methylprednisolone 1 mg/kg IV twice daily or equivalent dexamethasone (e.g., 10 mg IV every 6 hours). Continue corticosteroids use until the event is Grade 1 or less, then taper over 3 days.
 
• If no improvement, within 24 hours, consider starting tocilizumab or manage as Grade 4 (below)
 

Grade 4: Life-threatening symptoms: 
 
• Requirement for ventilator support OR
 
• Grade 4 organ toxicity* (excluding transaminitis)
 
	
 
• Administer methylprednisolone 1000 mg IV per day for 3 days; if improves, then manage as above.
 
• Consider alternate immunosuppressants if no improvement or if condition worsens.
 

Source: (Lee, 2019) (EMA, 2018)

## 10.8 APPENDIX 8: TLS TOXICITY MANAGEMENT

**Note these are guidelines that might require modification based on clinical circumstances of each subject and consider institutional standard of care treatment protocols, and failure to exactly follow these guidelines is not a protocol deviation or violation as follows:**

Tumor lysis syndrome (TLS) is an oncology emergency that occurs as a result of rapid tumor cell breakdown and the consequent release of massive amounts of intracellular contents, including potassium, phosphate, and uric acid, into the systemic circulation. These metabolic disturbances lead to life-threatening conditions and may cause sudden death if not treated. TLS commonly occurs following initiation of cytotoxic treatment in patients with high-grade lymphomas or acute lymphoblastic leukemia. Spontaneous cases involving both solid and hematologic tumors have also been reported. Rarely, TLS occurs following treatment with irradiation, corticosteroids, hormonal therapy, or biologic therapy. It is necessary to identify subjects at risk for TLS early in order to initiate preventive measures. In the event that preventive measures fail, the clinical parameters and signs of TLS must be understood and recognized so that treatment can begin as soon as possible, as this condition is a significant cause of morbidity and mortality.

When tumor cells are rapidly broken down and their contents released into the extracellular space, the released ions and compounds can cause metabolic disturbances too great to be neutralized by the body's normal mechanisms. The syndrome characterized by these metabolic derangements is known as TLS. TLS can cause life-threatening conditions and even death unless appropriately and immediately treated.

[figure not shown]
The Cairo-Bishop definition provided specific laboratory criteria for the diagnosis of TLS, as well as a grading system for describing the degree of severity of TLS ([Cairo, 2010](#)). Laboratory TLS is defined as any two (or more) of the following abnormalities:

- Serum uric acid level  $\geq 8$  mg/dL, or 25% increase from baseline.
- Serum potassium level  $\geq 6$  mmol/L, or 25% increase from baseline.
- Serum phosphate level  $\geq 6.5$  mg/dL in children and  $\geq 4.5$  mg/dL in adults, or 25% increase from baseline.
- Serum calcium level  $\leq 7$  mg/dL, or 25% decrease from baseline.

All these abnormalities must occur within 7 days after the dosing with SUPLEXA.

[Table 10](#) provides recommendation for prevention and treatment of TLS according to the subject's risk level as shown in Figure 6. Investigator should consider institution standard of care treatment protocols. Subjects will likely need to be aggressively hydrated with IV fluids. The target diuresis is at least 100 to 200 mL/hour (similar to the prophylaxis rate). Loop diuretics or mannitol may be used in conjunction with aggressive fluid-loading to promote aggressive diuresis. Furosemide can be used for this purpose in dosages of 20 to 100 mg IV every 4 to 8 hours or as an IV infusion of 10 to 20 mg/hour. Allopurinol, urate oxidase, and possibly urinary alkalinization all have a role in management. Ultimately, dialysis may also be needed, especially if a subject exhibits severe or refractory acute renal failure and/or symptoms from the metabolic derangements.

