- **Subsequent weekly infusions (after dose 3 with SUPLEXA batch 1 and batch 2)**

After completion of the first 3 weekly SUPLEXA batch 1 infusions, based on emerging data from prior subjects, disease evaluation (as described below), the discretion of the Investigator, and in agreement with the subject, treating physician and the Sponsor's Medical Monitor (or designee), the treatment period of SUPLEXA may be extended as follows:

Subjects will continue to receive SUPLEXA treatments of approximately 5 B cells, every 2 weeks with a wider window -1 day to +7 days until either, a) depletion of SUPLEXA batch 1 doses \*, or b) disease progression is assessed by the Investigator per iRECIST v1.1, or c) unacceptable toxicity, or other reasons for discontinuation as described in Section [7.2](#).

The 5 B cells will be provided as two bags of SUPLEXA targeted at 2.5B cells until all product used, unless there is only a single dose unit left, upon which time the subject may receive a single bag until more SUPLEXA is manufactured for them.

An additional SUPLEXA batch #2 may be manufactured for a subject based on (a) last dose of batch 1 and the investigator and subject and sponsor agree, then prior to the administration of the last SUPLEXA dose, blood can be drawn for SUPLEXA manufacturing of batch 2; or (b) > 2 weeks and < 8 weeks after the last dose of SUPLEXA administered, blood is collected for batch 2.

Note that subjects enroled in SUPLEXA-101, Version 3.0 or 2.0, and had SUPLEXA manufacturing started on or before October 31, 2022, may logistically be unable to have the consecutive administration of the recommended dosing regimen. These patients are therefore exempt from the defined gap in dosing, and the sequential dosing regimen described above. However, upon possible restarting additional doses of SUPLEXA, the dosing must be sequential until either, a) depletion of SUPLEXA batch 1 doses \*, or b) disease progression is assessed by

the Investigator per iRECIST v1.1, or c) unacceptable toxicity, or other reasons for discontinuation as described in Section 7.2.

Subjects will be monitored at the clinic for at least 90 minutes (+/- 30 min) after each infusion for AE and ISR.

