Disease evaluation by Response Evaluation Criteria in Solid Tumours (RECIST) v1.1 and immune RECIST (iRECIST) (solid tumours only)		X h			X i		X i	X i	X i	h. Scans within 4 weeks of screening will be accepted. i. Using standard of care scan schedule for the specified solid tumour. The first radiographic scan after receiving SUPLEXA will be performed at Week 6-12 weeks after the 1st SUPLEXA infusion and thereafter every 6-12 weeks depending on tumour type and as clinically indicated per investigator's discretion.

Study period	Screening		Treatment Period (Weekly dosing)		TREATMENT GAP	Treatment Extension Period	Follow Up after last dose		Notes	
			SUPLEXA Batch 1							
Study Treatment Week	-5	-5 to -1	First 3 infusions	Additional doses 		Doses 				
Visit Window (days)		±2		±2		60	-1 to +7	±5		
			Week 0 Day 1/ Baseline	1, 2			Every 8 weeks up to 48 weeks from last dose	EOS/ET	End of Study (EOS) will be conducted within 30d for all subjects who completed the study per protocol; Early termination (ET) visit will be conducted within 30d or subjects who withdraw from the study prematurely.	
Disease evaluation for haematologic malignancies only		X		X*		X*	X*	X	*As clinically indicated, may also be conducted every 4 weeks, starting 4 weeks after the 3 rd dose	
Complete blood count (CBC) with differential and blood chemistry	X		X j	X j, k	X j	X j	X	X	Refer to Table 5 for list of parameters to be evaluated j. Predose k. Repeat at baseline in local hospital lab for stat results, and central lab sample to be shipped	
Collect blood for pharmacodynamic immune assessments, including cytokines			X	X	X	X	X l		Refer to Section 8.4 for list of parameters to be evaluated l. collected where possible post dose	

Study period	Screening		Treatment Period (Weekly dosing)		TREATMENT GAP	Treatment Extension Period	Follow Up after last dose		Notes	
			SUPLEXA Batch 1							
Study Treatment Week	-5	-5 to -1	First 3 infusions	Additional doses 		Batch 2				
			Week 0 Day 1/ Baseline	1, 2		Doses 				
Visit Window (days)		±2		±2	±2	-1 to +7	60	-1 to +7	Every 8 weeks up to 48 weeks from last dose	EOS/ET
Serology		X m							Refer to Table 5 for list of parameters to be evaluated	

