Syphilis screening test		X							m. HIV positivity is disqualifying as this might be amplified in ex vivo stimulation	
Pregnancy test (WOCBP only)		X							Women of childbearing potential (WOCBP) Negative test must be performed within 72 hours prior to first study intervention	
Urinalysis		X	X n			X n			Refer to Table 5 for list of parameters to be evaluated	
Blood sample for SUPLEXA manufacturing	X o				X p				o. Batch 1: Subjects who will have adequate evidence of blast formation at the manufacturing facility (notification of yield will be 5 days after the blood collection), will proceed to next Screening	

Study period	Screening		Treatment Period (Weekly dosing)		TREATMENT GAP	Treatment Extension Period	Follow Up after last dose		Notes	
			SUPLEXA Batch 1							
Study Treatment Week	-5	-5 to -1	First 3 infusions	Additional doses 		Batch 2				
Visit Window (days)		±2		±2		Doses 	Every 8 weeks up to 48 weeks from last dose	EOS/ET		
Pre-treatment prophylaxis			X	X	X				visit. Subjects with insufficient yields will be considered screen failures and will be replaced.	
SUPLEXA administration IV			X q	X q	X r		X r		
p. Batch 2: After completion of Batch 1 and if subjects are eligible to continue to receive SUPLEXA, batch number 2 manufacturing and processing will take place.
 
The following pretreatment regimen is suggested, although a different regimen based on local standard of care/institutional practices is permitted: Administer acetaminophen 1000 mg (PO) for potential fever, diphenhydramine 12.5 mg PO (for potential rash) and allopurinol (100 mg) IV or PO for potential TLS in subjects who are at intermediate risk for TLS approximately 1 hour (60 min ± 20 min) before SUPLEXA infusion. Refer to Section 6.8.1 and 10.8Section 10.8 for further details.
 
q. Weekly 2.5 billion cells r. Additional treatment every 2 weeks at 5.0 B cells will be the investigator's assessment and in
	

Study period	Screening		Treatment Period (Weekly dosing)		TREATMENT GAP	Treatment Extension Period	Follow Up after last dose		Notes	
			SUPLEXA Batch 1							
Study Treatment Week	-5	-5 to -1	First 3 infusions	Additional doses 		Batch 2				
Visit Window (days)		±2		±2		Doses 				
			Week 0 Day 1/ Baseline	1, 2			Every 8 weeks up to 48 weeks from last dose	EOS/ET		

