##### **4.1.2.2 Subsequent Weekly Infusions (SUPLEXA Batch 1 and Batch 2)**

After completion of the first 3 weekly SUPLEXA batch 1 infusions, based on emerging data from prior subjects, disease evaluation (as described below), the discretion of the Investigator, and in agreement with the subject, treating physician and the Sponsor's Medical Monitor (or designee), the treatment period of SUPLEXA may be extended as follows:

Subjects will continue to receive SUPLEXA treatments of approximately 5 B cells, every 2 weeks with a wider window -1 day to +7 days until either, a) depletion of SUPLEXA batch 1 doses \*, or b) disease progression is assessed by the Investigator per iRECIST v1.1, or c) unacceptable toxicity, or other reasons for discontinuation as described in Section 7.2.

The 5 B cells will be provided as two bags of SUPLEXA targeted at 2.5B cells until all product used, unless there is only a single dose unit left, upon which time the subject may receive a single bag until more SUPLEXA is manufactured for them.

An additional SUPLEXA batch #2 may be manufactured for a subject based on (a) last dose of batch 1 and the investigator and subject and sponsor agree, then prior to the administration of the last SUPLEXA dose, blood can be drawn for SUPLEXA manufacturing of batch 2; or (b) > 2 weeks and < 8 weeks after the last dose of SUPLEXA administered, blood is collected for batch 2.

Note that subjects enroled in SUPLEXA-101, Version 3.0 or 2.0, and had SUPLEXA manufacturing started on or before October 31, 2022, may logistically be unable to have the consecutive administration of the recommended dosing regimen. These patients are therefore exempt from the defined gap in dosing, and the sequential dosing regimen described above. However, upon possible restarting additional doses of SUPLEXA, the dosing must be sequential until either, a) depletion of SUPLEXA batch 1 doses \*, or b) disease progression is assessed by the Investigator per iRECIST v1.1, or c) unacceptable toxicity, or other reasons for discontinuation as described in Section 7.2.

Subjects will be monitored at the clinic for at least 90 minutes (+/- 30 min) after each infusion for AE and ISR.

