### 6.1 STUDY INTERVENTION ADMINISTERED

ARM Name	Active
Primary Intervention Name	SUPLEXA therapeutic cells (referred to as SUPLEXA throughout)
Type	Autologous cellular therapy comprised of ex vivo activated autologous PBMC comprised predominantly of NK, NKT, $\gamma\delta$ T cells, and T cells of both CD8-positive and CD4-positive types stored in cryogenic media.
Dose Formulation	PlasmaLyte with 28 mM glucose, 3.5% human serum albumin, 50% EZ-CPZ (a proprietary cryopreservative medium) and 10% dimethyl sulfoxide
Unit Dose Strength	Billion cells
Dosage Level(s)	Each subject in each cohort will receive a target 2.5 billion SUPLEXA cells (range 1.3 to 3.1 billion cells) per infusion of 100 mL of cryogenic preservative solution.
Route of Administration	IV
Administration instructions	
Administer weekly (QW) <math>\pm 2</math> days for the first 3 weekly infusion and thereafter weekly with a range of -1 day to +7 days.
 
For prophylactic pre-treatment, refer to Section 6.8.1.
 
Thaw a SUPLEXA IV infusion bag.
 
Into the SUPLEXA IV infusion bag, slowly transfer approximately 250 mL (250 grams) of diluent PlasmaLyte (<math>\pm 20\%</math> is within the acceptable range; i.e., 200-300 grams or mLs). Allow the fluid to transfer by gravity.
 
Infuse each individual bag's full volume within 60 minutes into the subjects.
 
Where doses of 2 bags (5B cells) is given the same process and time is used. Thus, infusion of 2 bags is within 2 hours (120min).
 
Subjects may ambulate after infusion is complete.
 
For the first 3 weekly infusions:

ARM Name	Active
	
 
The first 3 subjects in each cohort will be monitored closely at the clinic for at least 6 hours after each of the first 3 weekly infusions and be contacted by phone on a daily basis (weekdays) between weekly infusions for up to 5 days post the 3rd treatment.
 
After the first three subjects , any subject receiving SUPLEXA will require a minimally 90minute (+/- 30min) post infusion observation and will be monitored for any AEs and immediate post infusion reaction(s).
 
 
Refer to Pharmacy manual for detailed administration instructions.

Sourcing	Autologous SUPLEXA therapeutic cells are manufactured, labelled, stored, and distributed by selected Contract Manufacturing Organisation.

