#### **6.5.1 Dose Modifications and Individual Stopping Rules due to DLT**

All eligible subjects are planned to receive a minimal cumulative dose of approximately 7.5 billion cells of SUPLEXA administered as target of 2.5 billion cells per individual SUPLEXA doses. The first 3 doses will be administered at least 1 week apart (unless delayed due to DLTs as described below) at Day 1 (baseline), Week 1 and Week 2.

During the study, the cumulative dose of study intervention will not be modified unless triggered by rules governing DLT (as described below); that is, subjects experiencing a DLT which does not resolve within 3 weeks or 2 DLTs may only receive 1 or 2 infusions, each 2.5 billion cells (for these subjects, cumulative dose may range between 2.5 billion cells to 5.0 billion cells).

[figure not shown]
The DSMB will convene to review all available data collected during the DLT assessment period(s) including Investigator's impressions and provide an additional layer of oversight. The DSMB will make recommendations to the Sponsor on enrolment modifications.

The rules below will apply independently to the solid tumours and haematologic malignancies in parallel and for each subject in the study.

1. Enrol a subject and administer 1st dose on Day 1. Assess for DLTs during the first DLT assessment period (1 week post 1st infusion).
  - a) No DLT, continue to 2nd dose at Week 1 (Day 8) – refer to item 2 below,
  - b) Subject experienced a DLT (per DLT criteria in Section 6.5) and the event resolved within 3 weeks to baseline levels (Grade 1 or lower)?
    - i) Yes, continue to 2nd dose – refer to item 2 below
    - ii) No, permanently discontinue study intervention and subject will continue to be followed-up as part of the study (unless withdraw consent and start other anti-cancer therapies) as described in Section 7.2.
2. Administer 2nd dose. Assess for DLTs during the 2nd DLT assessment period (1 week post 2nd infusion)
  - a) No DLT, continue to 3rd dose – refer to item 3 below

- b) Subject experienced a DLT (per DLT criteria in Section 6.5)
  - i) If first occurrence of DLT and the event resolved within 3 weeks to baseline levels (Grade 1 or lower)?
    - Yes, continue to 3rd dose – refer to item 3 below

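### Section 6.1 gives a weekly interval after dose 3, contradicting the two-weekly 5-billion-cell regimen set everywhere else in the protocol

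*Combined protocol and SAP*

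**What the plan says.** All subjects start with three infusions about a week apart, each with a target of 2.5 billion cells. What follows depends on the section.

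- Section 4.1.2.2: "Subjects will continue to receive SUPLEXA treatments of approximately 5 B cells, every 2 weeks with a wider window -1 day to +7 days". The synopsis carries the same rule, and Section 4.3 justifies up to 14 such infusions at two-week spacing.
- Schedule of Activities, note r: "Additional treatment every 2 weeks at 5.0 B cells".
- Section 6.1, administration row: after the first three infusions, "thereafter weekly with a range of -1 day to +7 days". Its dosage row gives only the 2.5-billion target per infusion, yet its instructions also cover the larger dose: "Where doses of 2 bags (5B cells) is given the same process and time is used".

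Weekly labels remain on the two-weekly part of the regimen. The synopsis heads it "Subsequent weekly infusions (after dose 3 with SUPLEXA batch 1 and batch 2", the title of Section 4.1.2.2 says the same, and the Schedule of Activities puts a weekly-dosing header over the treatment period, apparently spanning the additional-dose columns.

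For the secondary note, Appendix 8 (Section 10.8) defines laboratory tumour lysis syndrome (TLS) as two or more abnormalities in uric acid, potassium, phosphate or calcium, and adds: "All these abnormalities must occur within 7 days after the dosing with SUPLEXA". In the Schedule of Activities the row "Complete blood count (CBC) with differential and blood chemistry" is marked pre-dose on dosing days.

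**The concern.** Section 6.1 tells the site how to give the product. In a first-in-human study its interval should not differ from the one in the design section and the visit schedule. The difference arises where the dose per infusion doubles from 2.5 to 5 billion cells. A site that takes the interval from Section 6.1 and the dose from Section 4.1.2.2 would give 5 billion cells weekly, a regimen that no section justifies. A site that takes both from Section 6.1 would give 2.5 billion cells weekly, which is also not the planned extension regimen. Either way, the exposure behind the safety data would differ from the one described, and it would be unclear whether this was a protocol deviation.

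The interval also determines when the next chemistry sample is taken, because that sample is tied to the next dose. This is why the laboratory-TLS window comes in as a side issue.

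**Working it through.** The protocol states no figure to reproduce. The check is a comparison of permitted days and doses.

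**Interval after dose 3**

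- Section 6.1: 7 - 1 = day 6 to 7 + 7 = day 14, nine permitted days.
- Synopsis and Section 4.1.2.2: 14 - 1 = day 13 to 14 + 7 = day 21, nine permitted days.
- The two ranges share only days 13 and 14. Days 6 to 12, seven of the nine that Section 6.1 permits, are too early under the two-weekly text. Days 15 to 21 are too late under Section 6.1.

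**Dose intensity at the nominal intervals**

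| Reading | Dose and interval | Per week | Over 28 days |
|---|---|---|---|
| Intended regimen | 5 billion every 14 days | 5/2 = 2.5 billion | 2 x 5 = 10 billion |
| Section 6.1 dosage row with its weekly interval | 2.5 billion every 7 days | 2.5 billion | 4 x 2.5 = 10 billion |
| Two-bag dose with the Section 6.1 interval | 5 billion every 7 days | 5 billion | 4 x 5 = 20 billion |

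Only the third reading raises dose intensity, by a factor of 20/10 = 2. The second keeps the intensity but gives four infusions of half the size instead of two.

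**Secondary: scheduled chemistry against the 7-day window**

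The sample that follows a dose is the pre-dose sample of the next infusion or, after the last dose, the first follow-up visit.

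- Doses 1 and 2: the nominal next dose is 7 days later, inside the window. With the visit window of 2 days either way, the range is days 5 to 9, of which 5, 6 and 7 are inside. Section 6.5.1 says "The first 3 doses will be administered at least 1 week apart"; combined with the +2 day limit this gives days 7 to 9, of which day 7 is inside.
- Dose 3 onward, two-weekly: days 13 to 21, so 0 of 9 permitted days are inside. The earliest falls 13 - 7 = 6 days after the window closes.
- Last dose: 56 - 5 = day 51 to 56 + 5 = day 61, outside, unless an end-of-study or early-termination visit happens to fall sooner.
- If Section 6.1's weekly interval applied instead, days 6 and 7 of days 6 to 14 would be inside, 2 of 9.

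These are counts of permitted days, not probabilities of a visit on each day.

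**The case against.** The best defence of Section 6.1 is that the weekly wording is a leftover. Four other places agree on two weeks, the -1 to +7 day window already matches the two-weekly rule, and Section 6.1 refers to a pharmacy manual, not among these documents, that may be right. The intended regimen is indeed not in doubt. But the conflicting sentence stands in the current administration instruction, and neither the column header nor the section headings correct it.

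A reader might infer that Section 6.1 orders double the dose intensity. The documents do not support that. Its dosage row gives 2.5 billion cells per infusion, and weekly dosing at that level equals the intended intensity. Its two-bag sentence concerns process and infusion time, not interval. The doubling needs the dose from one place and the interval from another.

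A reader might also infer that the chemistry schedule is deficient for TLS. That goes too far:

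- Appendix 8 says when abnormalities count, not when blood must be drawn. It is expressly guidance, and its Table 10 asks for no specific diagnostic measures in low-risk disease. The risk-class figure is not available here, so the share of subjects at higher risk is unknown.
- The plan excludes listed high-TLS-risk disease, suggests allopurinol for intermediate risk, allows unscheduled tests (Section 10.2), requires clinically significant abnormal values to be repeated (Section 8.2.4), and collects adverse events to 30 days after the last dose. Symptomatic TLS can still be captured.
- An under-count of the Section 7.1 trigger is not shown: it needs related events of Grade 3 or higher, and the documents do not grade asymptomatic laboratory TLS at that level.
- Section 4.1.2.2 does name TLS-related laboratory values for treatment extension, but as clinically significant findings, within a list of alternatives, not through the Appendix 8 definition.
- Section 9.3.3 plans no laboratory-TLS output, so no planned table is wrong.

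Nor should the gap be expressed as a share of a maximum of 17 infusions. Section 4.3's 3 + 14 infusions would end at week 2 + 14 x 2 = 30 before any batch gap, whereas the synopsis gives up to 24 weeks for two optimal batches.

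**Conclusion.** The contradiction is real and should be corrected. On its own, Section 6.1 permits the next infusion on days 6 to 14 where the rest of the protocol requires days 13 to 21. Nominal dose intensity would reach twice the intended level only if the two-bag dose were given at the weekly interval. This assumes that the two-weekly regimen is the intended one, as the synopsis, note r, Section 4.1.2.2 and Section 4.3 all indicate. It does not apply to subjects from protocol versions 2.0 and 3.0 whose manufacturing began by October 31, 2022, to the extent that Section 4.1.2.2 exempts them from the sequential regimen.

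The laboratory-TLS point stands only as a limit on interpretation. Doses 1 and 2 are covered on the nominal schedule. From dose 3 on, the two-weekly regimen schedules no sample in the window. The absence of recorded laboratory TLS at 5 billion cells would therefore be informative only for infusions with an unscheduled or chance sample within 7 days.

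**What to change.** 1. In the Section 6.1 administration row, change the interval after the first three infusions from weekly to every 2 weeks, keeping the -1 to +7 day window.
2. In the Section 6.1 dosage row, add that doses after dose 3 are about 5 billion cells, given as two bags, or as one bag if only one remains.
3. Remove the word weekly from the headings for the later infusions in the synopsis and Section 4.1.2.2, and from the Schedule of Activities header where it covers the additional-dose columns.

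All three are wording changes, with no effect on sample size, visits or planned analyses. The pharmacy manual should be checked for the same interval when they are made.

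No change to the chemistry schedule is required. If the study report comments on laboratory TLS at 5 billion cells, it should use as denominator the infusions that had a chemistry sample within 7 days after the dose. This costs one count from data already collected.
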